## ABBREVIATIONS

Abbreviation	Definition
AH	Alcoholic Hepatitis
AE	Adverse Events
ALT	Alanine Aminotransferase (also known as glutamate-pyruvate transaminase-SGPT)
ANA	Anti-nuclear Antibody
ANOVA	Analysis of Variance
AST	Aspartate Aminotransferase (also known as glutamate-oxaloacetate transaminase-SGOT)
AUDIT	Alcohol Use Disorder Identification Test
BMI	Body Mass Index
BP	Blood Pressure
BUN	Blood Urea Nitrogen
CBC	Complete Blood Count
CHMP	Committee for Medicinal Products for Human Use
cm	Centimeter
CMV	Cytomegalovirus
CNS	Central Nervous System
COPD	Chronic Obstructive Pulmonary Disease
CRSU	Clinical Research Services Unit
CPS	Cytokine Release Syndrome
CPK	Creatine Phosphokinase
CRF	Case Report Form
DF	Discriminant Function
DSMB	Data and Safety Monitoring Board
ECG	Electrocardiogram
ELISA	Enzyme-Linked Immunosorbent Assay
EOT	End of Treatment
FACS	Fluorescence Activated Cell Sorter
GCP	Good Clinical Practice
GLP	Good Laboratory Practice
GMT	Geometric Mean Titer
H	Hours
HBsAg	Hepatitis B Surface Antigen
HBV	Hepatitis B Virus
HB Ab	Hepatitis B Antibody
HCT	Hematocrit

HCV Ab	Hepatitis C Virus Antibody
HDPE	High-density polyethylene
HGB	Hemoglobin
hCG	Human Chorionic Gonadotropin
HR	Heart Rate
ICF	Informed Consent Form
ICH	International Conference on Harmonization
IgE	Immunoglobulin E
IgG	Immunoglobulin G
IgM	Immunoglobulin M
IL-12	Interleukin-12
INR	International Normalized Ratio
IP	Investigational Product
IMP	Investigational Medicinal Product
IR	Immediate Release
IRB	Institutional Review Board
K	Potassium
kg	Kilogram
LAR	Legally Authorized Representative
LDH	Lactate Dehydrogenase
LDL	Low Density Lipoprotein
LPS	Lipopolysaccharide
MCH	Mean Corpuscular Hemoglobin
MCHC	Mean Corpuscular Hemoglobin Concentration
MCV	Mean Cell Volume
MELD Score	Model for End Stage Liver Disease Score
MLN	Mesenteric Lymph Nodes
µg	Microgram
mg	Milligram
Min	Minute
mL	Milliliter
N/A	Not Applicable
Na	Sodium
NOAEL	No Observable Adverse Event Level
NYHA	New York Heart Association
°c	Degrees Centigrade
PBMCs	Peripheral Blood Mononuclear Cells
PBS	Phosphate Buffered Saline
PI	Principal Investigator
PT	Prothrombin Time
QA	Quality Assurance
R&D	Research and Development
RBC	Red blood cells

SAE	Serious Adverse Event
SAS	Statistical Analysis System
SD	Standard Deviation
SOFA	Sequential Organ Failure Assessment
SOP	Standard Operating Procedure
SUSAR	Suspected Unexpected Serious Adverse Reaction
TNF	Tumor Necrosis Factor
ULN	Upper Limit of Normal
WBC	White Blood Cells
WHO	World Health Organization
w/w	Weight for weight

## PROTOCOL SYNOPSIS

**TITLE:** A Multicenter Randomized, Double-Blind, Placebo-controlled Dosing, Safety and Efficacy Study of IMM 124-E (Hyperimmune Bovine Colostrum) for Patients with Severe Alcoholic Hepatitis

**INVESTIGATIONAL PRODUCT:** IMM 124-E Hyperimmune Bovine Colostrum

**INDICATION:** Treatment of Severe Alcoholic Hepatitis (SAH)

**PHASE OF DEVELOPMENT:** 2a - Proof of Mechanism

### OBJECTIVES:

To determine:

1. The safety of orally administered Imm 124-E in patients with severe alcoholic hepatitis being treated with steroids
2. If orally administered Imm 124-E reduces endotoxemia and markers of activation of the innate immune system in patients with severe alcoholic hepatitis being treated with steroids
3. The efficacy of orally administered Imm 124-E in patients with severe alcoholic hepatitis being treated with steroids

**STUDY DESIGN:** This is a multi-center, randomized, placebo-controlled, double-blind, multiple dose study comprising three groups, 22 patients in each group.

**TREATMENT:** Subjects with severe AH (MELD  $\geq 20$  but  $\leq 28$ ) about to receive prednisolone/prednisone (40 mg/day x 28 days) will be randomized 1:1:1 to receive either Imm 124-E at 2400 mg/day or 4800 mg/day orally or matching placebo for 28 days. Standard of care nutrition support and alcohol cessation recommendations will be provided to all subjects. Alcohol withdrawal will be managed per standard of care.

Eligible patients will be randomly allocated to Imm 124-E or placebo as follows:

- Group A: Imm 124-E 2400 mg in two divided doses daily (plus placebo, see below for further details)
- Group B: Imm 124-E 4800 mg in two divided doses daily

- Group C: Placebo twice daily

**NUMBER OF SUBJECTS (PLANNED):** 66 patients with 22 patients in each of the above defined study groups

**DIAGNOSIS AND MAIN CRITERIA FOR INCLUSION:**

**Diagnosis:** Severe Alcoholic Hepatitis (SAH) is defined as:

Well accepted clinical criteria of jaundice and abnormal liver chemistry in appropriate setting with other corroborative findings such as hepatomegaly and leukocytosis

History of heavy alcohol use: Average daily alcohol intake of > 40 g in women and > 60 g in men for a minimum period of 6 months

MELD score > 20

**Key inclusion criteria:**

Eligible patients must fulfil the following inclusion criteria:

- Men and women age 21 and above
- Severe Alcoholic hepatitis with MELD score  $\geq 20$  and  $\leq 28$
- About to initiate prednisolone treatment, < 7 days of steroid treatment, or treatment naïve.
- Actively consuming alcohol within 6 weeks of entry into the study
- Willing and able to comply with study requirements
- Subjects or their legally authorized representatives (LAR) who have provided voluntary written informed consent.

**Key exclusion criteria:**

- Cow milk allergy, severe lactose intolerance and/or known or suspected allergy to any of the ingredients in IMM 124-E
- Other or concomitant cause of liver disease (Viral hepatitis, autoimmune liver disease, metabolic liver disease, vascular liver disease).
- Subjects who are known to be HIV positive.
- Active infection or sepsis (pneumonia by X-ray, positive blood or urine culture) Untreated spontaneous bacterial peritonitis based on > 250 polymorphonuclear (PMN) cells or positive culture. All subjects with enough ascites to be deemed safe for paracentesis, will undergo this procedure (as standard of care) to exclude spontaneous bacterial peritonitis.
- Acute kidney injury with serum creatinine > 1.5 mg/dl at time of randomization
- Evidence of acute pancreatitis (by imaging and lipase > 5 x ULN)
- Subjects who are pregnant or lactating
- Significant systemic or major illness that, in the opinion of the Investigator, would preclude the patient from participating in and completing the study.

- Subjects who are non-cooperative or unwilling to sign consent form.
- Active Gastrointestinal bleeding (e. g. hematemesis, melena)

(See body of protocol for full list of exclusions)

**TEST PRODUCT(S), DOSE AND MODE OF ADMINISTRATION:** The placebo and IMM-124E will both be presented as 1200mg of powder for reconstitution in Plastic Aluminium Foil Poly Laminate Pouches (sachets). The appearance of the active and placebo will be indistinguishable. Each subject will take two sachets each morning and then again in the evening. Consequently, each arm of the study will take the same number of doses per day. Subjects in:

- Group A (IMM-124E 2400mg/day) will receive one sachet of active and one sachet of placebo in the morning and again in the evening.
- Group B (IMM-124-E 4800 mg/day) will receive two sachets of active in the morning and again in the evening.
- Group C (Placebo - High protein milk powder) will receive two sachets of placebo in the morning and again in the evening.

**DURATION OF TREATMENT:** 28 Days

**DISCONTINUATION FROM TREATMENT OF INDIVIDUAL SUBJECT:**

Reasons for interruption/discontinuation include the following:

- Grade 3 or 4 toxicity considered related to study medication (laboratory abnormalities must be confirmed within 3 days)
- The investigator may withdraw a subject from the study at any time if he/she considers that remaining in the study compromises the subject's health or the subject is not sufficiently cooperative.
- The study DSMB may ask that a subject be withdrawn from the study if it considers that remaining in the study compromises the subject's health and after discussing the issue with the Principal Investigator.

**DISCONTINUATION OF ENTIRE STUDY**

- The entire study may be discontinued due to unexpected adverse events and with guidance from DSMB and NIAAA.

**ENDPOINTS:**

*Mechanistic Endpoints:*

- The sample size is based on a decrease in plasma endotoxin levels (adjusting for baseline) as measured by analysis of covariance across the study groups. This was

chosen based on the mechanism of action of Imm 124-E. The hypothesis is that both active-drug groups are superior to placebo. In prior studies, we have found the standard deviation of endotoxin levels to be 8-10%

- markers of gut permeability
- intestinal inflammation (calprotectin)
- TNF- $\alpha$  and other immune-inflammatory markers
- microbiome-metagenome

*Efficacy related endpoints:*

- number of subjects meeting Lille failure criteria at day 7
- mortality at 30 days, 90 days and 180 days,
- time to drop in conjugated bilirubin by 50%
- change in MELD and sequential organ failure assessment scores and Discriminant Function
- serum bile acids
- liver function tests

*Safety related endpoints:*

- incidence and severity of gastrointestinal events, including nausea, vomiting and diarrhea
- Proportion of subjects who develop renal failure, encephalopathy or pulmonary compromise
- Frequency of sepsis
- Frequency of any other adverse events

**SAFETY ENDPOINTS:**

No unexpected treatment related SAEs are expected throughout the participation period and the follow up period. It is anticipated that majority of the patients will be initially hospitalized; thus, the initial hospitalization or prolongation of hospitalization will not be considered as serious adverse event in this study. Please see "Adverse Events" section of the protocol for further information concerning AE's and SAE's.

**STATISTICAL ANALYSIS:**

This study is designed to evaluate dose response and appropriateness of endpoints for further work. All measured variables and derived parameters will be listed individually and, if appropriate, tabulated by descriptive statistics. For descriptive statistics, summary tables will be provided giving sample size, absolute and relative frequency by study group and sample size, arithmetic mean, standard deviation, coefficient of variation (if appropriate), median,

minimum and maximum, percentiles, p-values, and 95% CI (Confidence Interval) by study group for means of continuous variables.

**Chi-square test or Fisher's Exact test** (as appropriate) will be applied for testing the statistical significance of the difference in percent of subjects reporting adverse events between the study groups.

**Paired T-Test or Signed Rank test** (as appropriate) will be applied for testing the statistical significance of the changes from baseline in laboratory results within each study group.

**ANOVA model** will be applied for testing the statistical significance of the difference in the changes in laboratory results between the study groups.

**ANOVA model** will be applied for testing the statistical significance of the difference in immunological markers and the secondary endpoint parameters between the study groups.

**Dunnett's method** will be used for comparing each of the active groups to the Placebo group. Changes in immunological markers and efficacy parameters may be assessed across each individual subject.

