**22 subjects will be recruited to each of the three arms.**

### Other Mechanism of action related endpoints

- Intestinal permeability (stool  $\alpha$ 1 antitrypsin): Previous studies have indicated that alcoholic liver disease is associated with increased intestinal permeability. We will measure intestinal permeability, as measured by the stool  $\alpha$ 1 antitrypsin level across the two study arms correcting for baseline values using analysis of covariance. We will not plan any formal hypothesis testing because there are no prior data to guide sample size estimates etc.
- Intestinal inflammation (stool lactoferrin and calprotectin, ELISA): These are considered to be markers of intestinal inflammation. They will also be analyzed using a similar approach as noted above. We will compare the levels across both arms correcting for baseline values for these continuous variables, which we anticipate will be normally distributed.
- Systemic inflammation: We will measure the following:

A: C reactive protein

B: 4-OH nonenal and malondialdehyde (oxidative stress markers)

C: cytokines: Innate immunity- TNF- $\alpha$ , IL6, Inflammasome- IL1 $\beta$ , TH1- interferon-gamma, TH2- IL-10, IL-4, Treg-IL17, IL23 (these will be run on a multiplex machine but are subject to ongoing funding from NIAAA for these analyses).

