### **Subject Disposition**

Missing values will be explained in individual data tables. No procedures for replacing missing values by estimates will be implemented.

If there is scientific evidence or explanation for one or more outliers, this will be presented together with a statistical test for outlier identification. In case of outliers, the corresponding statistical analysis will be provided with and without these values.

Any deviation from the original statistical plan will be described and justified in the study report.

**Primary endpoint:** The incidence and severity profile of adverse events will be reported for those receiving Imm-124 versus placebo. It is expected that there will be no signals for increased adverse events with Imm-124. The adverse event rates will be enumerated for each group. Proportions of subjects with specific adverse events will be compared using Fisher Exact test. However, no formal hypothesis testing is planned as there is no basis to expect any changes across groups.

**Principal secondary endpoint:** The principal secondary endpoint will be the decrease in plasma LPS (endotoxin) levels (adjusting for baseline) as measured by analysis of covariance across the study groups. This was chosen based on the mechanism of action of Imm 124-E. The hypothesis is that both active-drug groups are superior to placebo. In prior studies, we have found the standard deviation of LPS levels to be 8-10%.

**Subgroup Analysis:** We will perform subgroup analysis based on gender, race, baseline MELD and SOFA scores, and presence or absence of encephalopathy. Given the overall sample size, we do not anticipate having enough power to do meaningful hypothesis testing. We will also do

a multivariable regression analysis of outcomes with these as covariates to determine if they have an independent impact on outcome, and to identify any interaction terms between these covariates and treatment arm. These are primarily designed for hypothesis generation.

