## **Safety Analysis**

Safety will be assessed by descriptive statistics of AEs and laboratory tests. The incidence of reported AEs and the values of laboratory tests from all subjects will be presented with and without regard to causality based on the Investigator's judgment.

Adverse events will be coded according to MedDRA and presented in tables by system organ class, MedDRA preferred term and study group. Adverse events will be summarized by treatment group to provide visual comparison among the treatment groups with respect to incidence of adverse events (the number of subjects reporting at least one episode of a specific adverse event), incidence of adverse events by severity within body system, incidence of adverse events by attribution within body system, and incidence of adverse events causing withdrawal and incidence of serious adverse events. Regarding severity and attribution summaries, the most extreme outcome (highest severity and closest to study drug related) will be used for those subjects who experience the same adverse event on more than one occasion.

Written narratives will be provided for all serious, unexpected or other significant adverse events that are judged to be of special interest because of their clinical importance.

Chi-square test or Fisher's Exact test (as appropriate) will be applied for testing the statistical significance of the difference in percent of subjects reporting adverse events between the study groups.

Paired T-Test or Signed Rank test (as appropriate) will be applied for testing the statistical significance of the changes from baseline in laboratory results within each study group.

ANOVA model will be applied for testing the statistical significance of the difference in the changes in laboratory results between the study groups. Dunnett's method will be used for comparing each of the active groups to the Placebo group. Adverse Events

All tests will be two-tailed, and a p value of  $\leq 5\%$  will be considered statistically significant.

The data will be analyzed using the SAS ® version 9.1 (SAS Institute, Cary North Carolina).

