## **Data Safety Monitoring Board**

An independent Data and Safety Monitoring Board (DSMB) to be established by the NIH and TREAT consortium to assess at intervals the progress of a clinical trial, the safety data, and the critical safety endpoints, and to recommend to the NIH whether to continue, modify, or stop a trial.

**Anticipated Outcomes:** Means for continuous variables at end of study will be analyzed adjusting for baseline values using ANCOVA. Proportions will be compared using chi square or Fisher's Exact test. We expect to show a greater decrease in mean circulating LPS levels in those receiving Steroids+ Imm 124-E compared to steroids + placebo. We further expect to demonstrate that those receiving Imm 124-E will have a reduction in MELD, DF, intestinal permeability, markers of intestinal inflammation, markers of dendritic cell activation, pro-inflammatory T-cell and cytokine profile, cholestasis (serum bile acids) and bilirubin.

**Additional pathophysiologic insights:** Microbiome-metagenomic-immunologic-transcriptomic-histologic data from will lend themselves to analyses using a "systems biology approach" to determine how interactions between these contribute to severe AH and how Imm 124-E can modify this. These will provide novel insights on the role of the metagenome in AH and provide additional targets for therapy in the future.

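### The synopsis puts secondary endpoints, including endotoxin, under ANOVA while the endpoint text specifies ANCOVA; align the model and give endotoxin one multiplicity rule and one main visit

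*Combined protocol and SAP*

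**What the plan says.** **Where ANOVA is named.** The synopsis (Statistical Analysis) applies ANOVA to changes in laboratory results. A second ANOVA sentence there "will be applied for testing the statistical significance of the difference in immunological markers and the secondary endpoint parameters between the study groups". Safety Analysis repeats the laboratory part: "ANOVA model will be applied for testing the statistical significance of the difference in the changes in laboratory results between the study groups". None of these sentences mentions a baseline covariate.

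**Where baseline adjustment is specified.** Subject Disposition defines the principal secondary endpoint as the "decrease in plasma LPS (endotoxin) levels (adjusting for baseline) as measured by analysis of covariance across the study groups", and the synopsis Endpoints section says the same. Anticipated Outcomes (under Data Safety Monitoring Board) is general: "Means for continuous variables at end of study will be analyzed adjusting for baseline values using ANCOVA". For intestinal permeability, Other Mechanism of action related endpoints compares the "level across the two study arms correcting for baseline values using analysis of covariance", then adds "We will not plan any formal hypothesis testing because there are no prior data to guide sample size estimates etc". Secondary Endpoints (endotoxin), Interpretation of Labs (immune markers) and Analysis Population (MELD, discriminant function, liver function) also adjust for baseline without naming the model.

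**Error rate.** Determination of Sample Size sets 0.025 because of multiple comparisons, for LPS on placebo against either active arm. The synopsis and Safety Analysis say Dunnett's method "will be used for comparing each of the active groups to the Placebo group". Safety Analysis ends with "All tests will be two-tailed, and a p value of" 5% or less counting as significant.

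**Visits.** Secondary Endpoints lists endotoxin at Days 7 and 28. Table 2 samples it at D0, D7 and D30. The principal secondary endpoint paragraph names no visit.

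**The concern.** Endotoxin is a secondary endpoint, so the synopsis sentence on secondary endpoint parameters covers it and gives it a model different from the one in its own definition. Subject Disposition requires deviations from the statistical plan to be described and justified. With two models on paper, it would be unclear afterwards which analysis was the deviation.

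Two further details of the same analysis are not settled where it is defined: which multiplicity rule applies, and which of two visits carries the result. For laboratory results there is no such contradiction within the safety text. The issue there is precision, since ANOVA of change makes weaker use of baselines that are already collected, in a trial of 22 per arm.

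**Working it through.** **1. The plan's own sample size.** Inputs are from Table 4. The two-sided normal formula per arm is n = 2(z_α/2 + z_power)² (SD/difference)².

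- Scenario 1 (α 0.05, power 90%, difference 25, SD 10): 2(1.960 + 1.282)² × 0.16 = 3.4, so 4 (stated 5).
- Scenario 2 (0.025, 80%, 25, 25): 2(2.241 + 0.842)² = 19.0, so 20 (stated 20).
- Scenario 3 (0.025, 90%, 45, 25): 2(2.241 + 1.282)² × (25/45)² = 7.7, so 8 (stated 7).
- Scenario 4 (0.025, 90%, 25, 25): 2(2.241 + 1.282)² = 24.8, so 25 (stated 26).

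All agree within one patient. The 22 per arm lies between Scenarios 2 and 4, so the sizing rests on a 0.025 comparison of each dose with placebo.

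**2. Multiplicity at one visit.** Two doses share one placebo group, with 22 per arm and 66 − 3 = 63 error degrees of freedom. Familywise error is by simulation under no effect. Power per dose uses a difference of 25 and SD 25, so the noncentrality is 1/√(2/22) = 3.32.

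| Rule | Familywise error | Power per dose |
|---|---|---|
| Dunnett, familywise 5% (critical value 2.26, about 0.027 per comparison) | 5.0% | 85% |
| 0.025 for each dose | 4.6% | 84% |
| 0.05 for each dose | 9.0% | 90% |

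The first two rules are practically the same. Only the third reading differs materially.

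**3. Precision for laboratory changes.** Let ρ be the baseline to follow-up correlation and k the follow-up SD divided by the baseline SD. The documents give neither, so both are assumed.

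- Variance of change is proportional to 1 + k² − 2ρk.
- ANCOVA residual variance is proportional to (1 − ρ²)k².
- The large-sample ratio is (1 − ρ²)k² / (1 + k² − 2ρk). At k = 1 this is (1 + ρ)/2.

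| k | ρ = 0.3 | ρ = 0.5 | ρ = 0.7 |
|---|---|---|---|
| 0.75 | 0.46 | 0.52 | 0.56 |
| 1 | 0.65 | 0.75 | 0.85 |
| 1.5 | 0.87 | 0.96 | 1.00 |

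The denominator minus the numerator is (1 − ρk)², so the gain vanishes when ρk = 1. Estimating the slope multiplies the ANCOVA variance by about 1 + 1/61 = 1.016 with 22 per arm. The k = 1 row becomes 0.66, 0.76 and 0.86. At k = 1.5 and ρ = 0.7 the ratio is about 1.01, a negligible loss. At k = 1 the confidence intervals are narrower by 1 − √0.66 = 19%, 1 − √0.76 = 13% and 1 − √0.86 = 7%.

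**4. Visits.** Endotoxin is not sampled after D30 in Table 2, so the only end-of-study value that Anticipated Outcomes can mean is the later one. That paragraph goes on to name a fall in mean LPS as the expected result. This points to the later visit, but no sentence makes it the main one. Safety Analysis uses a Day 28-30 label for antibody samples, so Day 28 and D30 may be one window.

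**The case against.** The strongest reply is that the endotoxin model is already settled. A specific definition outranks a general synopsis sentence, and Anticipated Outcomes repeats ANCOVA. That stands as to which text should govern, and so the synopsis sentence is the one to change. It does not remove the contradiction, because both statements sit in the same synopsis.

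It can also be said that ANOVA of change is valid for laboratory data in a section described as mainly descriptive. That stands too; the case there is precision alone.

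On error rate, the sample-size section does tie 0.025 to LPS, and the 5% follows a Dunnett sentence closely enough to be read as its familywise level. The conflict is therefore one of clarity.

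Several stronger readings are tempting but unsupported:

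- A reader might infer that MELD and discriminant function are tested by ANOVA. No sentence says so. They are exploratory, and Analysis Population already adjusts them for baseline.
- A reader might credit endotoxin with a power gain from ANCOVA. ANCOVA is already its specified analysis, and the 25% SD may already be the adjusted one.
- A reader might quote 8.5% to 9.7% error from testing both visits with Dunnett (assumed between-visit correlation 0.7 to 0), or 6.6% to 7.9% from keeping whichever model wins. Both depend on decision rules the plan does not contain.
- A reader might see a conflict between either dose (null hypothesis, sample size) and both doses (hypothesis statements). The first frames the comparisons and the second the expected direction. For a non-primary endpoint this is mostly missing detail.

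**Conclusion.** The point holds as an inconsistency that should be corrected, at modest severity: endotoxin is secondary in a Phase 2a trial, but it is the endpoint behind the 22 per arm. The synopsis ANOVA sentence contradicts the ANCOVA specified for it.

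For laboratory changes, ANCOVA would have about 0.65 to 0.85 of the variance of ANOVA of change in large samples, and 1 to 2% more than that with 22 per arm. This assumes equal SDs and correlations of 0.3 to 0.7; at other SD ratios the gain can be larger or nil.

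Dunnett and 0.025 are interchangeable in practice. Naming one matters only because the 5% read per comparison would give about 9% familywise error at one visit. The documents do not show that the planned endotoxin analysis inflates its error rate, and the main visit is partly indicated already.

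**What to change.** - **Synopsis Statistical Analysis and Safety Analysis:** replace ANOVA with ANCOVA (three-level treatment plus the baseline value) for continuous laboratory, marker and endotoxin endpoints. Keep marker analyses hypothesis-generating, as Interpretation of Labs and the mechanism section already intend, and report them as estimates with confidence intervals.
- **Subject Disposition, principal secondary endpoint:** attach Dunnett at two-sided familywise 5% to the endotoxin ANCOVA, each dose against placebo. Align the 0.025 in Determination of Sample Size with it, and say that the 5% in Safety Analysis is not a per-dose threshold for endotoxin.
- **Secondary Endpoints and Table 2:** reconcile Day 28 with D30. Before unblinding, name the main endotoxin visit and report the other as supportive. The choice is the sponsor's.

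**Cost.** Wording changes and one sponsor decision; the baselines are already collected. One visit becomes supportive, and the covariate uses one degree of freedom (63 to 62), which moves the Dunnett critical value from 2.262 to 2.263.
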